9.4. Human Immunodeficiency Virus Testing and Vaccine Induced Seropositivity

9.4.1. Human Immunodeficiency Testing

HIV testing will be performed as indicated in the [Time and Events Schedule](#).

At screening and baseline, subjects will be tested for HIV infection, and must be negative to be entered into the study. If possible, the site should select an assay that is US FDA-approved.

At all other main study visits that include HIV-testing, a study-specific HIV-testing algorithm (detailed in the Laboratory Manual) will be followed. Information provided to the clinical staff of the study site will not include the results of specific tests, but will state only the final interpretation as “infected” or “uninfected”. This system allows timely HIV testing without compromising the double-blind nature of the study. The algorithm used for HIV testing throughout the main study aims to differentiate false-positive results (Vaccine Induced Seropositivity [VISp]) from true positives (HIV infection).

During the optional LTE phase, the study-specific HIV-testing algorithm described above will be followed as long as treatment assignment is blinded. Upon study unblinding, unblinded HIV and VISp results will be reported.

If a false-positive HIV test result develops during the study, further VISp testing will be offered via post-study follow-up (see Section [9.4.3](#)).

9.4.2. Management of Subjects who Become HIV-infected During the Study

Test results performed to confirm the diagnosis will be forwarded to the study staff. Subjects who become HIV infected during the study, including the optional LTE phase, will be (see Section [12.3.3](#)):

- Excluded from further vaccinations.
- Provided counseling and referred for medical treatment.
- Informed about observational studies monitoring subjects with HIV infection.
- Excluded from initiation of the optional LTE phase.

9.4.3. VISp

In general, HIV-uninfected subjects who participate in preventative HIV-vaccine studies may develop HIV-specific antibodies as a result of an immune response to the candidate HIV vaccine, referred to as VISp. These antibodies may be detected in common HIV-serologic tests, causing the test to appear positive even in the absence of actual HIV infection. Vaccine Induced Seropositivity may become evident during the study or after the study has been completed.

Should an HIV-Ab test give a positive result for a particular subject during the study, the central lab will carry out a follow-up testing algorithm either to exclude or confirm HIV infection. Further details of this algorithm are given in the Laboratory Manual.

Subjects should not donate blood during the study. Blood donation options for those subjects who wish to resume blood donation after the study will be explained at the final study follow-up visit.

In the case of VISP, if, either during the study or after the end of the study, a subject requires an HIV test outside the study (eg, to obtain a travel visa or insurance, or for medical reasons), he/she should contact the research center. The center can issue a written statement giving details on VISP and on the testing algorithm to be followed. If requested by a subject, repeat HIV testing will be available at the site at most every 3 months to confirm their HIV status. It is highly preferable that this repeat HIV testing will be performed at the research center. More frequent testing is only allowed after sponsor approval. Testing for a particular subject will be available as long as VISP is present for this subject.

Depending on the local availability of a follow-up protocol, subjects could join into such a study that specifically follows the course of VISP. Such a study may not be available at all sites. However, if such a study is not available, the site will provide HIV testing on request as described in the previous paragraph.

In addition to providing testing, subjects will always receive pre- and post-test counseling.

9.4.4. Social Impact

Subjects in preventive HIV-vaccine clinical studies may experience problems with personal relationships, employment, education, health care, housing, health, disability or life insurance, travel, and immigration. In relation to a subject's family, friends, and/or colleagues, the social impact could manifest in one or more ways, resulting in social conflicts and stigmatization:

1. The investigational vaccine is thought to be harmful to the subject's health, including a belief that it might cause HIV infection.
2. The subject is perceived as HIV infected or at high risk.
3. Repercussions from any VISP.

For these reasons, subjects will complete a social impact questionnaire (at the timepoints specified in the [Time and Events Schedule](#)) to evaluate any potential consequences of the subject's participation. For more information, please refer to the Study Procedures Manual.

9.5. Sample Collection and Handling

The actual dates and times of sample collection must be recorded in the CRF or laboratory requisition form.

See the [Time and Events Schedule](#) for the timing and frequency of all sample collections.

Instructions for the collection, handling, storage, and shipment of samples are found in the Laboratory Manual that will be provided. Collection, handling, storage, and shipment of samples must be under the specified, and where applicable, controlled temperature conditions as indicated in the Laboratory Manual.

10. SUBJECT COMPLETION/DISCONTINUATION OF STUDY TREATMENT/WITHDRAWAL FROM THE STUDY

10.1. Completion

A subject who is not participating in the optional LTE phase will be considered to have completed the study if he or she has completed the assessments at Week 72. A subject who is participating in the optional LTE phase will be considered to have completed the main study if he or she has completed the assessments at Week 72 and will be considered to have completed the optional LTE phase if he or she has completed the assessments at the last visit of the optional LTE phase at Week 216 (for subjects who consent to be followed-up for approximately 3 years after Week 72) or Week 264 (for subjects who consent to be followed-up for approximately 4 years after week 72).

10.2. Discontinuation of Study Treatment

Subjects will be withdrawn from study vaccine administration for the reasons listed below. These subjects must not receive any additional dose of study vaccine but should enter the follow-up phase with assessments of safety and immunogenicity. The subject will be encouraged to complete the post-vaccination follow-up visits of the last vaccination received and a 12 and 24 weeks follow-up visit after the last vaccination received, specified as Week 60 and Week 72 in the [Time and Events Schedule](#). Additional unscheduled visits may be performed for safety/tolerability reasons, if needed. In case the subject withdraws before receiving the first vaccination, the subject is not required to attend follow-up visits. In case of questions, the investigator is encouraged to contact the study responsible physician. Subjects who prematurely discontinue study treatment are not eligible for the optional LTE phase.

- Unblinding
- Anaphylactic reaction following vaccination
- Pregnancy
- Any related SAE
- Any related AE, worsening of health status or intercurrent illnesses that, in the opinion of the investigator, requires discontinuation from study vaccine
- Confirmed HIV infection
- Chronic or recurrent use of immunosuppressants (after discussion with the sponsor)
- Missing more than 1 study vaccination
- Any event (eg, overdose, incorrect dosing) that, in the opinion of the investigator (in agreement with the sponsor), would require discontinuation of study vaccine

10.3. Contraindications to Vaccination

The following events constitute a contraindication to vaccination at that point in time. If any of these events occur at the scheduled time for vaccination, the vaccination can be rescheduled (as long as this is in agreement with the allowed windows, see Section [9.1.2](#)):

- Acute illness at the time of vaccination. This does not include minor illnesses, such as diarrhea or mild upper-respiratory tract infection.
- Fever (oral temperature $\geq 38.0^{\circ}\text{C}$) at the time of vaccination.

10.4. Withdrawal From the Study

Each subject has the right to withdraw from the study at any time for any reason without affecting the right to treatment by the investigator. The investigator should make an attempt to contact subjects who did not return for scheduled visits or follow-up. Although the subject is not obliged to give reason(s) for withdrawing prematurely, the investigator should make a reasonable effort to ascertain the reason(s) while fully respecting the subject's rights.

A subject will be withdrawn from the study for any of the following reasons:

- Lost to follow-up
- Withdrawal of consent
- Death
- Repeated failure to comply with protocol requirements
- Decision by the sponsor or the investigator to stop or cancel the study
- Decision by local regulatory authorities and Institutional Review Board/Independent Ethics Committee to stop or cancel the study

If a subject is lost to follow-up, every reasonable effort (at least 2 documented attempts to contact the subject by telephone and at least one documented written attempt) must be made by the study-site personnel to contact the subject and determine the reason for discontinuation/withdrawal. The measures taken to follow-up must be documented.

When a subject withdraws before completing the study, the reason for withdrawal is to be documented in the CRF and in the source document. Study vaccine assigned to the withdrawn subject may not be assigned to another subject. Subjects who are vaccinated and who withdraw will not be replaced. If a subject withdraws early from the study, assessments for early withdrawal should be obtained (see Section 9.1.7).

Subjects who wish to withdraw consent from participation in the study will be offered a single Exit visit for safety follow-up (prior to formal withdrawal of consent). They have the right to refuse. The exit visit is only applicable to the main study until Week 72.

10.5. Withdrawal From the Use of Samples in Future Research

The subject may withdraw consent for use of samples for research (see Section 16.2.5). In such a case, samples will be destroyed after they are no longer needed for the clinical study. Details of the sample retention for research are presented in the main ICF.

11. STATISTICAL METHODS

Statistical analysis will be done by the sponsor or under the authority of the sponsor. A general description of the statistical methods to be used to analyze the safety and immunogenicity data is outlined below. Specific details will be provided in the Statistical Analysis Plan.

11.1. Subject Information

For all subjects, demographic characteristics (eg, age, height, weight, body mass index [BMI], race, and gender), and other baseline characteristics (eg, medical history, concomitant diseases) will be tabulated and summarized with descriptive statistics.

11.2. Analysis Populations

The safety population will consist of all subjects who received at least one dose of study vaccine, and for whom any post-dose data is available.

The immunogenicity population will consist of all subjects who received at least one dose of study vaccine, and who have data from at least one evaluable post-dose blood sample.

The per protocol immunogenicity population will consist of all randomized and vaccinated subjects for whom immunogenicity data are available, excluding subject samples with major protocol deviations expecting to impact the immunogenicity outcomes (for example missed vaccinations, natural infections, etc).

11.3. Sample Size Determination

The sample sizes in the main study are regarded to be appropriate to assess the safety and tolerability of the different vaccine regimens. Placebo recipients are included for blinding and safety purposes and will provide control specimens for immunogenicity assays.

While mild to moderate vaccine reactions (local site and systemic responses) are expected, AEs that preclude further vaccine administration or more serious ones that would limit product development are not anticipated. With 110 individuals in the tetravalent Ad26.Mos4.HIV vaccine regimen, the observation of 0 such reactions would be associated with a 95% confidence that the true rate is <2.7%. For the combined active groups (n 165), there would be 95% confidence that the true rate is <1.8% when 0 events are observed. The following table shows the probabilities of observing at least one AE given true AE rates.

True AE Rate	Probability of Observing at Least one AE in n Subjects		
	n = 55	n = 110	n=165
0.1%	5%	10%	15%
0.5%	24%	42%	56%
1%	42%	67%	81%
2.5%	75%	94%	98.5%
5%	94%	99.6%	>99.9%
10%	99.7%	>99.9%	>99.9%

The primary population for the safety analyses will consist of all subjects who received at least 1 dose (Ad26.Mos.HIV, Ad26.Mos4.HIV, or placebo).

Anticipating a dropout rate of approximately 10%, the sample sizes will allow detection of approximately 1.5-fold differences in Env-binding Ab titers between the groups with Ad26.Mos4.HIV (approximately 100 evaluable subjects) and their corresponding group with Ad26.Mos.HIV only (approximately 50 evaluable subjects); with 80% probability, assuming a 1-sided 5% Type I error and a standard deviation of 0.4 on the \log_{10} scale.

The immunogenicity population will consist of all subjects who received at least 1 dose and have at least 1 measured post-dose blood sample collected.

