11.4. Immunogenicity Analyses

Descriptive statistics (actual values and changes from reference with 95% confidence interval) will be calculated for continuous parameters. Frequency tabulations will be calculated for discrete parameters. Graphical representations of changes in immunologic parameters will be made as applicable.

No formal hypothesis on immunogenicity will be tested. The analysis of immunogenicity will be done on the (per protocol) immunogenicity population as defined in Section [11.2](#).

Differences between groups at a specific time point will be tested for exploratory purposes by a 2-sample t-test if the data appear to be normally distributed. If not, the non-parametric Wilcoxon rank sum test will be used. If portions of the measurements are censored below the assay quantification limit, the Gehan-Wilcoxon test will be employed. All statistical tests will be 2-sided and will be considered statistically significant if $p<0.05$.

Frequency tabulations will be calculated for discrete (qualitative) immunologic parameters. Significant differences between groups will be determined by a 2-sided Fisher's exact test.

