## 1. INTRODUCTION

This statistical analysis plan (SAP) was initially written to describe the analyses of the main part of the study (up to Week 72). This updated version covers also the reporting of data collected till the end of the long-term extension (LTE) which lasted up to Week 264 (final analysis at end of study) for the group 2A receiving the full vaccination regimen ‘Ad26.Mos4.HIV/Ad26.Mos4.HIV + gp140’. At the time this SAP was written the Week 72 statistical analysis was already performed and will not be rerun. The below described analyses will be performed on fully unblinded data.

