### 1.4. Sample Size Justification

See CTP, Section 11.2.

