### 6.3. Immune Response Analysis

No formal hypothesis on immunogenicity will be tested however at week 28 the differences between the 2 active groups (Ad26.Mos4.HIV + gp140/ Ad26.Mos.HIV + gp140) will be explored by means of a GMR including 95%CI and by a 2-sample t -test on the log data if those are normally distributed or by a Wilcoxon rank sum test otherwise. Those analyses will be performed on the following assays:

- ELISA: Clade C (C97ZA.012), Mos1
- ADCP: Clade C (C97ZA.012), Mos1
- ELISpot: Env peptide pool PTE, Gag peptide pool PTE, Pol peptide pool PTE

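### The 80% power for a 1.5-fold titer difference is a 1-sided 5% figure; the planned test is 2-sided 5%, where power is about 71%

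*Protocol*

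**What the plan says.** Protocol section 11.3, repeated in the synopsis under Statistical Methods, says that "the sample sizes will allow detection of approximately 1.5-fold differences in Env-binding Ab titers between the groups" receiving the tetravalent vaccine (about 100 evaluable) and the trivalent vaccine (about 50 evaluable), after roughly 10% dropout. The conditions are "with 80% probability, assuming a 1-sided 5% Type I error and a standard deviation of 0.4" on the log10 scale.

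Protocol section 11.4 covers the analysis of those titers. It names a 2-sample t-test, with rank-based alternatives for non-normal or censored data, and adds: "All statistical tests will be 2-sided and will be considered statistically significant" at p<0.05.

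SAP section 6.3 says that at Week 28 the difference between the two active groups "will be explored by means of a GMR including 95%CI" and by a 2-sample t-test on the log data, or a Wilcoxon test if the data are not normal. The Env ELISA results for Clade C (C97ZA.012) and Mos1 are on its list of assays.

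SAP section 1.4 gives no power figure. Its whole content is "See CTP, Section 11.2". In this protocol, 11.2 is Analysis Populations and sample size is 11.3.

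**The concern.** A power statement holds only for the test it was computed for. Section 11.3 sizes the antibody comparison with a 1-sided 5% criterion, and the next section rules that criterion out. A 95% CI for the ratio of geometric means corresponds to a 2-sided 5% test, so the SAP agrees with section 11.4 and not with 11.3. Neither document plans a 1-sided test or a 90% interval.

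Env-binding antibody is a primary endpoint, and section 11.3 is the only place that says how large a difference between the regimens this trial can detect. A reader faced with a non-significant comparison of 2A with 1A would use that sentence to judge how informative the result is. If the quoted power is too high for the test that was run, the reader will treat a null result as stronger evidence than it is.

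**Working it through.** **Inputs, all from protocol section 11.3**
- Difference: 1.5-fold, so δ = log10(1.5) = 0.1761
- SD: 0.4 on the log10 scale
- Evaluable subjects: 100 (2A) and 50 (1A)

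**Common quantities**
- SE = 0.4 × √(1/100 + 1/50) = 0.4 × √0.03 = 0.0693
- Noncentrality = 0.1761 / 0.0693 = 2.542, with 100 + 50 − 2 = 148 degrees of freedom

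**Step 1. Reproduce the stated figure (1-sided 5%)**
- Normal approximation: Φ(2.542 − 1.645) = Φ(0.897) = 81.5%
- Noncentral t: 81.2%
- Dropout of 10% taken literally (99 and 49.5), noncentral t: 80.8%
- Difference with 80% power, normal approximation: 10^[(1.645 + 0.842) × 0.0693] = 1.49-fold. The noncentral t also gives 1.49.

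The sponsor's 80% and its approximate 1.5-fold are right for a 1-sided 5% test.

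**Step 2. Same inputs, planned test (2-sided 5%)**
- Normal approximation: Φ(2.542 − 1.960) = Φ(0.582) = 72.0%
- Noncentral t: 71.4%
- Dropout of 10% taken literally, noncentral t: 71.0%
- Difference with 80% power, normal approximation: 10^[(1.960 + 0.842) × 0.0693] = 1.56-fold. The noncentral t gives 1.57.

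**Step 3. Is dropout the explanation?** Take all 110 and 55 randomized subjects as evaluable.
- SE = 0.4 × √(1/110 + 1/55) = 0.0661
- Noncentrality = 0.1761 / 0.0661 ≈ 2.67, with 163 degrees of freedom
- 2-sided power, noncentral t: 75.5%

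No attrition assumption brings the 2-sided test to 80% at 1.5-fold.

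| Evaluable (2A / 1A) | 1-sided 5% | 2-sided 5% |
|---|---|---|
| 100 / 50 | 81.2% | 71.4% |
| 99 / 49.5 | 80.8% | 71.0% |
| 110 / 55 | 84.4% | 75.5% |

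**Step 4. What this means for the reported interval.** The expected 95% CI is the estimated ratio divided and multiplied by 10^(1.976 × 0.0693) = 1.37.

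**Step 5. If the Wilcoxon test is used.** Assuming normal data and a relative efficiency of 0.955, 2-sided power at 100 and 50 is about 69%.

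**For scale only.** Holding 80% power at 1.5-fold with a 2-sided t-test would have needed about 124 and 62 evaluable subjects.

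**The case against.** The 1-sided basis is not hidden. It stands in the same sentence as the 80%, and the figure is right for it. Protocol section 1.2 expects better Clade C responses with the tetravalent vaccine, so sizing in one direction and then reporting 2-sided as the stricter convention would be an understandable choice. The comparison is exploratory, both documents disclaim a formal hypothesis, and section 11.3 opens by justifying the numbers on safety grounds. Every input is labelled approximate, and in terms of detectable difference the shift is only from 1.49-fold to 1.57-fold. The SAP also says that "the Week 72 statistical analysis was already performed and will not be rerun", so nothing in the conduct of the trial can change.

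Most of this bears on weight, and it does keep the weight moderate. It does not remove the mismatch. Section 1.2 states an expectation about responses, not a choice of test, and no passage says the sizing was deliberately 1-sided while the analysis would not be. The word approximate fits 1.49 but does not stretch to 1.57: even a true 1.54-fold difference has only 76.7% power at 2-sided 5%. Having chosen to state what the comparison can detect, the plan should state it for the test it specifies. A completed analysis is a reason to correct the record, not to leave it.

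**Conclusion.** The statement is wrong as written for the planned analysis and should be corrected. With SD 0.4 log10, about 100 and 50 evaluable subjects, and a 2-sample t-test, power for a 1.5-fold difference is about 71% at 2-sided 5%, about 10 points below the 81% that applies at 1-sided 5%. The chance of missing a true 1.5-fold difference is 1 − 0.714 ≈ 29%, against 1 − 0.812 ≈ 19% on the stated basis.

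The size of the gap rests only on the protocol's own inputs. Power would be lower still if the SAP's per-protocol immunogenicity set falls below 100 and 50. That set requires the first three vaccinations within specified windows, and the documents give no attrition figure for it. The safety justification in section 11.3 is unaffected. The wrong section number in SAP 1.4 is a clerical slip and adds nothing to the weight of this point.

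**What to change.** Restate the sentence in protocol section 11.3 and the synopsis or, if no further amendment is issued, in the study report. Suggested content:

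> With about 100 and 50 evaluable subjects after roughly 10% dropout and an SD of 0.4 log10, a 2-sample t-test at 2-sided 5% has about 71% power for a 1.5-fold difference, or 80% power for a difference of about 1.57-fold.

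Keep the SD and the test in the sentence, because the figures cannot be interpreted without them. If the 1-sided sizing was deliberate, say so, say that the analysis does not apply that criterion, and still give the 2-sided figure.

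Point SAP section 1.4 to protocol section 11.3.

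The cost is one sentence and one cross-reference. The stated power becomes less favourable. No subjects are added, and no analysis is changed or rerun.

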11.4. Immunogenicity Analyses

Descriptive statistics (actual values and changes from reference with 95% confidence interval) will be calculated for continuous parameters. Frequency tabulations will be calculated for discrete parameters. Graphical representations of changes in immunologic parameters will be made as applicable.

No formal hypothesis on immunogenicity will be tested. The analysis of immunogenicity will be done on the (per protocol) immunogenicity population as defined in Section [11.2](#).

Differences between groups at a specific time point will be tested for exploratory purposes by a 2-sample t-test if the data appear to be normally distributed. If not, the non-parametric Wilcoxon rank sum test will be used. If portions of the measurements are censored below the assay quantification limit, the Gehan-Wilcoxon test will be employed. All statistical tests will be 2-sided and will be considered statistically significant if $p<0.05$.

Frequency tabulations will be calculated for discrete (qualitative) immunologic parameters. Significant differences between groups will be determined by a 2-sided Fisher's exact test.

